1.0 Objectives / Specific Aims

Fenofibrate, a safe and long-established lipid-lowering agent, was recently discovered to have unexpected yet dramatic therapeutic effects on diabetic retinopathy (DR) in two large clinical trials (1,2). Intriguingly, the retinal benefits were independent of plasma lipids, suggesting novel mechanisms of action. Furthermore, evidence indicates that fenofibrate's beneficial effects extend to many other microvascular complications of diabetes.

Our aims are: 1) to recruit a cohort of 40 well-characterized fenofibrate-naïve patients with type 2 diabetes who will receive oral fenofibrate 160 mg/day for six weeks; this work will establish a clinical sample repository, collected immediately prior to and after treatment, to enable us to 2) characterize the global plasma proteome before and after fenofibrate treatment and future follow-up studies. We expect to gain novel insights into the systemic effects of fenofibrate on the pathophysiologic processes that drive diabetic vascular complications. This will generate new hypotheses about the common root causes of diabetic complications and complement data being accrued in ongoing studies of retinopathy, nephropathy, atherosclerosis, and complications of pregnancy that integrate human data with and animal/cellular model systems. The ultimate translational impact of the work will be the development of proactive means to block a range of complications early in their evolution, either through the development of more selective targeted therapies, and/or finding new disease indications for existing drugs.

To translate this into new preventive and/or therapeutic measures, we hypothesize: 1) that fenofibrate has mechanisms of action beyond PPAR α agonism that attenuate microvascular complications of diabetes; and 2) that observable treatment-induced changes in the constituents of plasma will reflect the underlying effects of the drug on target tissues.

2.0 Background

Work in my laboratory is directed at improving our understanding of the vascular complications of diabetes, and our work relates to vascular disease in general (i.e. to cardiovascular, cerebrovascular, and peripheral vascular disease).

The complications of diabetes, which range from well-recognized conditions such as DR, to less obvious ones such as hepatic steatosis and fibrosis, remain challenging and without truly satisfactory therapies. For example, DR is a leading cause of blindness worldwide, and with the ongoing epidemic of diabetes, promises to constitute a major global health problem for the foreseeable future. Current standard of care includes anti-VEGF antibodies and steroids (both via invasive intraocular injection), laser photocoagulation, and vitrectomy, all of which are useful only in the late stages of the disease. By that time, irreversible retinal damage has occurred, and some therapies actually involve further retinal destruction. Similar considerations apply to diabetic renal disease and neuropathy. Such 'crisis management' is necessary and valuable, but it would be vastly preferable to stop complications at an earlier stage using a convenient, safe, orally available drug. The recent discovery that fenofibrate is beneficial for DR and other microvascular complications (1,2) brings hope, and tantalizingly, the drug's efficacy across different complications suggests unrecognized common disease pathways (3-7). Still, the lack of correlation between its microvascular protective effects and its lipid-lowering activity raises questions (1,2). Presumably, the relevant mechanism(s) of action are unique to fenofibrate, a PPAR α agonist, and not shared with either PPAR γ agonists, e.g. rosiglitazone and pioglitazone, that enhance insulin sensitivity, or HMG-CoA reductase inhibitors (statins), that lower lipid levels by

upregulating hepatic LDL receptors. It is also unclear whether the benefits of fenofibrate are mediated via PPAR α or some novel mechanisms of action (8-13). In fact, recent data from our group using a human retinal pigment epithelial (RPE) barrier model showed that fenofibrate, but not other PPAR α agonists (WY14643, gemfibrozil, bezafibrate), attenuated the toxic effects of oxidized LDL on barrier integrity (14). Thus, fenofibrate may or may not be the answer, but it certainly provides important clues, and our lack of understanding of its systemic effects on the diabetic milieu is a barrier to the development of new treatments. Discovery of the mechanisms and pathways of action could yield a new generation of drugs that can protect multiple tissues from the effects of diabetes, blocking disease development proactively instead of reacting to end-stage complications.

3.0 Intervention to be studied

Fibrates belong to a class of drugs that exert their effects by activating peroxisome proliferator activated receptor α (PPAR α) (15). These drugs reduce the concentration of plasma triglyceride (TG) by 30-50% and raise the level of high-density lipoprotein cholesterol (HDL-C) by 2-20% (15-17). The first member of the class, clofibrate, was introduced in the 1960's and became available in the US in 1967 (18). Fenofibrate (the original generic name of which was proctofene), a third-generation fibrate, was introduced in clinical practice in 1975 (19). Fenofibrate is now one of the most commonly prescribed fibrates worldwide, indicated for the treatment of hypercholesterolemia, combined dyslipidemia, remnant hyperlipidemia, endogenous hyperlipidemia (hypertriglyceridemia) and mixed hyperlipidemia (Friedrickson type IIa, IIb, III, IV, and V dyslipidemia, respectively) (19).

Fenofibrate is FDA-approved for oral administration. The primary indication is for use in adult patients with hypercholesterolemia or mixed dyslipidemia. The standard dose of fenofibrate, 160 mg/day that was used in the ACCORD study (2) will be replicated in the current study. Fenofibrate is not FDA approved for the treatment of diabetic retinopathy.

4.0 Study Endpoints (if applicable)

Specific endpoints have not been predetermined.

5.0 Inclusion and Exclusion Criteria/ Study Population

Type 2 diabetes is highly prevalent in our endocrine clinic population and recruitment of sufficient numbers of volunteer subjects should be easily achieved. We anticipate recruitment of subjects to occur over six months, such that all study samples will be available for LC-MS/MS analysis within eight months of start-up. We have a long track record of collaboration with the SCTR NEXUS facility, e.g. through DCCT/EDIC, and are familiar with their policies and procedures. While our sample size is adequate for discovery research related to the systemic effects of fenofibrate treatment, any human study of outcomes would require a much larger cohort and longer period of follow-up. All subjects will be screened by their provider to ensure the eligibility for the study according to the criteria outlined below.

Inclusion criteria:

- Male or female aged ≥ 18 and ≤ 70 years

- Type 2 diabetes of at least one year's duration; stable glycemic control (no more than 1.0% change in HbA1c in the previous six months, but no limit on HbA1c)
- Triglycerides >150 mg/dL (in the previous six months)

Exclusion criteria:

- Previous use of Fenofibrate or other fibrates
- Pregnancy/lactation
- Active malignancy
- Recent cardiac event or congestive heart failure
- Active liver disease (LFT's > 2x's normal value)
- Significant renal impairment (serum creatinine > 2mg/dl)
- Current warfarin use

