8.0 Recruitment Methods

Participants will be approached by their treating physician (in this case either the PI or one of the co-investigators) from the patients attending the MUSC Endocrinology clinics.

Advertisements will be placed in MUSC Endocrinology clinics and MUSC elevators.

ResearchMatch.org will be utilized as a recruitment tool for this protocol. ResearchMatch.org is a national electronic, web-based recruitment tool that was created through the Clinical & Translational Science Awards Consortium in 2009.

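### The one-arm before/after change is the only contrast, yet Section 5 does not require unchanged lipid- or glucose-lowering medication before Visit 1; a stability criterion would be a cheap improvement.

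*Protocol*

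**What the plan says.** Sections 1 and 10 of the protocol describe one cohort of 40, all given fenofibrate for six weeks. A plasma proteome is taken from each participant before and after, and an enrichment analysis is then used to name the processes that treatment has altered. No control group, placebo or run-in is described.

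Section 5 contains one stability rule: "stable glycemic control (no more than 1.0% change in HbA1c in the previous six months, but no limit on HbA1c". The lipid criterion is a single threshold, "Triglycerides >150 mg/dL (in the previous six months", with no condition on treatment since that value. Two exclusions concern drugs: "Previous use of Fenofibrate or other fibrates" and "Current warfarin use".

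On recruitment, Section 8 says "Participants will be approached by their treating physician (in this case either the PI or one of the co-investigators", and Section 10 places consent at a routine endocrinology clinic visit. Visit 1 is scheduled afterwards, with no interval given. Section 10 has medications recorded at both visits. It does not mention start dates and attaches no rule to the record.

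**The concern.** With no concurrent comparison, the before/after change carries everything that differs between the two visits. The protocol recognises that stability matters, since it sets a rule for HbA1c. That rule is only a partial safeguard. HbA1c lags behind a treatment change and may move by up to 1.0%, so it does not exclude a recent change in glucose-lowering therapy. It says nothing about a lipid-lowering drug.

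The recruitment route makes the gap concrete. Candidates have had raised triglycerides and may have any HbA1c, and they are approached at a clinic visit at which therapy may be altered. A drug started there can still be taking effect between Visits 1 and 2. It would appear on both medication lists and so look unchanged. What is at stake is the attribution of part of the signature to fenofibrate. Eligibility is fixed in the protocol, so this is not a matter left to an analysis plan.

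**Working it through.** **The plan's own figure.** 40 participants × 2 visits = 80 proteomes, as Section 10 states. A stability criterion leaves both numbers unchanged.

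**Inputs.** n = 40 is from the protocol. All other inputs are assumptions, because the documents give no rate of recent medication change and no protein variances: the share affected, f = 5%, 10% or 20%; the shift in an affected participant, d = 0.5 or 1 SD of within-person change; 500 proteins; one set of 20 proteins; 200 sets.

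**Bias in the mean change** = f × d.
- d = 0.5: 0.025, 0.05 and 0.10 SD.
- d = 1: 0.05, 0.10 and 0.20 SD.

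For scale, the paired effect detectable with 80% power at an unadjusted two-sided 5% is (1.96 + 0.84)/√40 ≈ 0.44 SD.

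**One protein, no true fenofibrate effect.** Using the noncentral t with the mean shift taken as constant, shifts of 0.05, 0.10 and 0.20 SD give false-positive rates of 6.1%, 9.5% and 23.5% at an uncorrected 5%. With Bonferroni correction over 500 proteins, simulation gives at most 0.2%, which is negligible.

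**A 20-protein set, participant-level test.** This is a one-sample t-test on each participant's set mean. The SD of the set mean is √[(1 + 19ρ)/20], which is 0.22 at within-set correlation ρ = 0 and 0.49 at ρ = 0.2. Averaging therefore makes a common shift easier to detect, and correlation weakens that. Simulated flag rates for f = 5% / 10% / 20%, with all shifts in the same direction:

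| Case | Uncorrected 5% | Bonferroni over 200 sets |
|---|---|---|
| d = 1, ρ = 0 | 13% / 35% / 80% | 0% / 0.2% / 6% |
| d = 0.5, ρ = 0 | about 9% / 18–19% / 54% | below 0.1% / 0.2% / 3% |
| d = 1, ρ = 0.2 | 8% / 17% / 49% | 0.1% / 0.2% / 2% |

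If the direction is random from one affected participant to the next (d = 1, ρ = 0), the uncorrected rate is 5% / 5% / 5%, which is nominal. If the changes are spread over four drug classes, each acting on its own set, it is 5% / 7% / 12% per set.

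**Recruitment cost.** Candidates needed to enrol 40 = 40/(1 − f): 40/0.95 = 42.1, 40/0.90 = 44.4 and 40/0.80 = 50.

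**Timeline.** Section 5 plans six months of recruitment and says "all study samples will be available for LC-MS/MS analysis within eight months of start-up". Two months is 8.7 weeks; less the six-week course, 2.7 weeks remain for the last recruit.

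**The case against.** The strongest reply is that nothing here is wrong or contradictory. The study is hypothesis-generating, has no predetermined endpoints and already has a glycaemic stability rule. That stands, and it is why the point is an optional improvement.

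The size also depends on a demanding assumption: that every affected participant shifts in the same direction in the same proteins. Real changes would include starts and stops of different drugs, and then most of the inflation disappears. This stands too.

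Three stronger readings are tempting, and the documents do not support them.

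- **A large distortion of the enrichment results.** Under gene-permutation enrichment with a 1 SD shift and uncorrelated proteins, the Bonferroni-corrected rates are about 4% / 24% / 77%. At 0.5 SD they fall to about 0.4% / 2.5% / 21%. With ρ = 0.2 that procedure flags 36% of sets uncorrected, and 8.75% corrected, with no medication change at all. Section 10 names enrichment analysis but no permutation scheme. These figures should not carry the argument.
- **Recent changes can never be identified afterwards.** For clinic recruits the investigators may be the treating physicians, so prescribing history may be within reach. The medication record in Section 10 is also not an exhaustive field list. A sensitivity analysis leaving out recent changers may be possible for some. It is not assured: start dates are not named, and Section 8 also recruits through advertisements and a national web registry.
- **The study aims to separate fenofibrate from statins and PPAR γ agonists in this cohort.** Section 2 only presumes, as background on mechanism, that the relevant action is not shared with those classes.

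**Conclusion.** The point holds as a cheap improvement that the sponsor could make. Section 5 allows a lipid- or glucose-lowering drug to be started, stopped or changed shortly before Visit 1, and the only contrast would attribute its continuing effect to fenofibrate.

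The likely harm is modest and cannot be derived from the documents. It is negligible for single proteins after correction. For coordinated sets it is appreciable if results are read at an uncorrected 5% and the changes share a direction, but at most about 6% after correction over 200 sets by a participant-level test. It is near nominal if directions are mixed, and zero if nobody has a recent change. All of this rests on the assumed rates, shifts and set sizes.

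**What to change.** Add to the inclusion criteria in Section 5 that lipid-lowering and glucose-lowering medication has not been started, stopped or changed for a stated period before Visit 1. The investigators set the period; one matching the six-week treatment interval is an example, and nothing in the documents shows that it is sufficient. State which changes count, for instance whether routine insulin adjustment does. Confirm the criterion when medications are recorded at Visit 1. A candidate whose therapy was changed for clinical reasons is scheduled later or replaced. The text should say that clinical care is not delayed to meet the criterion, since recruiter and treating physician may be the same person.

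The cost is one eligibility line and a short re-check at Visit 1, with no extra visit, sample or proteome. Section 5 already says "All subjects will be screened by their provider to ensure the eligibility for the study". At 5%, 10% or 20% affected, about 42, 44 or 50 candidates would be needed for 40 enrolled, where Section 5 expects that "recruitment of sufficient numbers of volunteer subjects should be easily achieved". With only 2.7 weeks to spare, late candidates would have to be replaced rather than deferred by six weeks. The sample becomes slightly less representative of patients whose therapy is in flux.

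The criterion does not address medication changes after Visit 1, regression to the mean from selecting on triglycerides, or the lack of a control group.

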6.0 Number of Subjects

For this study, 40 patients (20 males and 20 females) aged 18-70 years, matching the ethnic composition representative of the demographics of SC, will be recruited from the cohort attending our Endocrinology Clinics at MUSC.

7.0 Setting

Participants will be recruited and consented at MUSC's Endocrinology clinic. Procedures at both visits will be performed at SCTR NEXUS nursing clinic.

8.0 Recruitment Methods

Participants will be approached by their treating physician (in this case either the PI or one of the co-investigators) from the patients attending the MUSC Endocrinology clinics.

Advertisements will be placed in MUSC Endocrinology clinics and MUSC elevators.

ResearchMatch.org will be utilized as a recruitment tool for this protocol. ResearchMatch.org is a national electronic, web-based recruitment tool that was created through the Clinical & Translational Science Awards Consortium in 2009.

9.0 Consent Process

Potential participants will be identified by treating physicians (PI/Co-PI's) from the patients attending the MUSC Endocrinology clinics. The PI and/or IRB-approved personnel will explain the nature of the study to individuals who meet criteria. Individuals who take part in this study must choose to participate voluntarily and must provide signed consent. Potential participants will be provided IRB-approved consent forms, the opportunity to read it, and the opportunity to ask questions. They will be consented before undergoing any study-related procedures. They will be encouraged to take time to discuss study participation with family and friends. Once the informed consent form is signed, participants will be actively enrolled in the study.

By an analogous process, written permission will be obtained for the HIPAA document. IRB approved personnel will give a copy of the signed informed consent form and the HIPAA form, to the participant. Informed consent forms will be signed, and copies distributed as usual (PI files and to the participant), with strict regard for confidentiality.

10.0 Study Design / Methods

Regularly scheduled Endocrinology clinic visit:

- If participants qualify and agree to participate, they will be provided an informed consent form, and a HIPAA form and provided the opportunity to sign agreement to participate.
- Visit one will then be scheduled for participants at the SCTR NEXUS clinic by the research coordinator.
- Participants will be instructed on fasting protocol following consent process and prior to visit one.

Visit 1:

[figure not shown]
- Upon arrival at the SCTR NEXUS clinic, a physical examination will be performed by either the PI or co-investigators. Clinical data will be recorded to include demographic information, diabetes complication status and medications, and anthropometric information.
- Women of childbearing potential will have urine β -HCG measured (+pregnancy outcome is criteria for exclusion) and will be required to use the following as acceptable methods for birth control throughout the study: 1) barrier methods including male and female condoms, diaphragm, cervical cap and contraceptive sponge, 2) hormonal methods including birth control pills, vaginal ring (NuvaRing), contraceptive implant (Nexplanon), contraceptive injection (Depo-Provera) and birth control patch, 3) intrauterine devices (IUDs) such as the copper IUD (ParaGard) and the hormonal IUD (Mirena, Skyla, Kyleena, others), 4) sterilization to include tubal ligation or the Essure system for women, and vasectomy for men, or 5) avoiding sexual activity that could cause you to become pregnant.
- Fasting blood (80ml) will be obtained for baseline labs (BUN, Cr, urine microalbumin, LFTs, CPK, Lipid Profile, HbA1c, TSH, C-peptide) and processed to yield heparin, EDTA, and citrate-plasma, serum, and pellets (sufficient for all planned analyses). A timed morning urine sample will be collected with the volume recorded. Samples will be stored in ultra-low freezers for proteomics and subsequent confirmatory assays (by ELISA).
- Participants will then be given the study medication (160 mg fenofibrate to be taken orally daily for six weeks) by the research physician. As well, they will receive instruction on possible side effects and proper protocol for reporting unexpected symptoms.
- Following venipuncture, participants will be given a choice of breakfast foods from which to choose by the IRB approved personnel and a place to eat.
- Participants will receive a gift card at the completion of visit one in the amount of \$25.
- Participants will be scheduled for visit 2 in six weeks.

Visit 2:

- Upon arrival at the SCTR NEXUS clinic, a physical examination will be performed by either the PI or co-investigators. Clinical data will be recorded to include demographic information, and medications, and anthropometric information.
- Fasting blood (80ml) will be obtained for follow-up labs (BUN, Cr, urine microalbumin, LFTs, CPK, Lipid Profile, HbA1c, TSH, C-peptide) and processed to yield heparin,

EDTA, and citrate-plasma, serum, and pellets (sufficient for all planned analyses). A timed morning urine sample will be collected with the volume recorded. Samples will be stored in ultra-low freezers for proteomics and subsequent confirmatory assays (by ELISA).

- Participants will then undergo an assessment of adverse events and study drug compliance, which will be determined by pill count.
- Following venipuncture, participants will be given a choice of breakfast foods from which to choose by the IRB approved personnel and a place to eat.
- Participants will receive a gift card at the completion of visit two in the amount of \$25.
- The plasma proteomic signature will be generated by LC-MS/MS (n=80 proteomes) of each subject before and after fenofibrate treatment. Bioinformatic approaches will then be employed based on geneset enrichment analysis to identify the biological processes/signaling networks impacted by treatment.

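### The contraception rule lets a hormonal method begin around the baseline draw, where a one-group before/after comparison cannot separate it from fenofibrate; the expected effect is small and the remedy cheap

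*Protocol*

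**What the plan says.** - **The rule.** It stands in Protocol section 10.0, among the Visit 1 procedures: women of childbearing potential "will be required to use the following as acceptable methods for birth control throughout the study". The list includes "hormonal methods including birth control pills, vaginal ring (NuvaRing), contraceptive implant (Nexplanon), contraceptive injection (Depo-Provera) and birth control patch". It also accepts barrier methods, intrauterine devices (copper or hormonal), sterilization, and abstinence: "or 5) avoiding sexual activity that could cause you to become pregnant".
- **The order of events.** Consent is taken at an earlier clinic visit, and Visit 1 is then scheduled; no interval is given. At Visit 1 the contraception item is followed by the fasting blood draw and then by dispensing: "Participants will then be given the study medication (160 mg fenofibrate to be taken orally daily for six weeks".
- **Entry criteria.** Section 5.0 has no contraception criterion. Its only stability requirement concerns HbA1c.
- **The comparison.** Section 1.0 aims to "characterize the global plasma proteome before and after fenofibrate treatment". Section 10.0 adds: "The plasma proteomic signature will be generated by LC-MS/MS (n=80 proteomes) of each subject before and after fenofibrate treatment". Enrichment analysis is then to identify processes affected by treatment. No control group is described, and section 4.0 fixes no endpoints.
- **Records.** Medications are recorded at both visits. A start date is not among the items listed.
- **Numbers.** Section 6.0 plans "40 patients (20 males and 20 females) aged 18-70 years". It does not say how many of the women will be of childbearing potential.

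**The concern.** Each participant's treatment effect is read from two samples six weeks apart. Anything else that begins at about the time of the first sample, and that alters plasma proteins or lipids, falls into the same difference. For most other medicines such timing would be chance. Here the protocol itself asks a woman without a method to adopt one around baseline, so the timing can be systematic.

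If she chooses a systemic hormonal method, her first sample is taken before, or only shortly into, the hormone, and her second after about six weeks of hormone and fenofibrate together. If hormones shift a group of proteins in the same direction, that is a pattern to which an enrichment analysis responds. The risk is that some of this shift is counted towards fenofibrate. A later analysis can drop or flag such women, but it cannot give them a clean baseline.

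**Working it through.** **The plan's own figure.** 40 subjects × 2 visits = 80 proteomes, as stated. There is no sample-size or power formula to reproduce.

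**Inputs**
- From the protocol: n = 40 in total, 20 of them women; one paired difference per subject.
- Assumed, because the documents give neither: k, the number of women who begin a systemic hormonal method at or near baseline; and D, the shift in a hormone-responsive protein in those women, in SDs of the paired difference. Range shown: k = 0 to 6, D = 1 to 3.
- Assumed: fenofibrate has no effect on that protein, and the test is a one-sample t-test of the paired differences at two-sided 5%. The protocol does not name this test; it serves as a yardstick.

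**Formulas.** The mean shift over the group is k × D / n. The starters also widen the spread: with p = k/n, the SD becomes about √(1 + p(1 − p)D²). The typical test statistic is then (kD/n) × √n / SD.

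- k = 1, D = 2: shift 1 × 2 / 40 = 0.05 SD; SD = √(1 + 0.025 × 0.975 × 4) = 1.05; statistic 0.05 × 6.32 / 1.05 = 0.30.
- k = 4, D = 2: shift 4 × 2 / 40 = 0.20 SD; SD = √(1 + 0.10 × 0.90 × 4) = 1.17; statistic 0.20 × 6.32 / 1.17 = 1.08.

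**False-positive rate by simulation**, 40,000 runs per setting, all 40 subjects:

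| k | Mean shift, D = 1 to 3 (SD) | D = 1 | D = 2 | D = 3 |
|---|---|---|---|---|
| 0 | 0 | 5.0% | 4.9% | 5.0% |
| 1 | 0.025–0.075 | 5.0% | 4.8% | 5.0% |
| 2 | 0.05–0.15 | 5.4% | 6.5% | 7.9% |
| 4 | 0.10–0.30 | 8.0% | 14.5% | 20.8% |
| 6 | 0.15–0.45 | 12.6% | 28.6% | 45.4% |

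One starter causes no inflation and two cause little. Four would matter, but four is one in five of all the women enrolled.

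**How likely are four?** This is again an illustration on assumed figures. If 10 of the 20 women were of childbearing potential and each had a 10% to 20% chance of starting a hormonal method, the binomial probability of four or more starters would be about 1% to 12%.

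**Women only.** At D = 2 the rate in the 20 women is 7.6% for k = 2, 20.2% for k = 4 and 44.5% for k = 6. These rates apply only if women are tested separately, which the protocol does not say.

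**The case against.** The strongest reply has five parts.

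1. *The rule does not cause a hormonal start.* This stands. Non-drug methods satisfy it equally, and fenofibrate is the only medicine the protocol dispenses. A reader might infer that the protocol itself brings a second drug in; the text only permits one.
2. *A start on the day of baseline is not established.* This also stands. Consent comes earlier, section 9.0 counts a participant as enrolled once consent is signed, and a rule that runs through the study may bind from then. But no interval is stated, so a method begun shortly before Visit 1 remains possible and could still be changing the measures between the two draws.
3. *Medications are recorded at both visits, so starters can be found.* Largely true. A method listed only at Visit 2 would show up. One begun just before Visit 1 would look established without a start date. Section 12.0 leaves no link to the participant after the study ends, so the date could not be asked for later.
4. *The statistical analysis plan may deal with starters.* It may, and its absence here is no finding. A reader might infer that the change will be reported as a fenofibrate effect; the protocol does not show that. What remains for the protocol is the timing of the baseline sample.
5. *The size has no anchor in the documents.* True of both k and D, and of the premise that hormones alter these proteins. The t-test also differs from the planned enrichment analysis. A set procedure that treats proteins as independent would respond more strongly to a shared shift, and one that tests at subject level would not.

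**Conclusion.** The point holds as a minor one. The text permits a systemic hormonal method to begin at or shortly before the baseline draw, and requires neither that it be established by then nor that it stay unchanged to Visit 2. In a woman who does this, a one-group before/after difference cannot separate the hormone from fenofibrate.

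The expected effect on the group result is small: none for one starter, about 5–8% against a nominal 5% for two, and about 8–21% for four. This rests on assumed shifts of 1 to 3 SD, an unknown number of starters, a single-protein test, and the general-pharmacology assumption that hormones change plasma proteins or lipids.

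The documents do not support the reading that fenofibrate findings in the women will be materially false. That would need several starters and a separate analysis by sex, and neither is stated.

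**What to change.** Keep the list of accepted methods as it is. Then:

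- State in sections 5.0 and 10.0 that any hormonal method must be established before the Visit 1 draw, with the lead-in set by the investigators, and kept unchanged until Visit 2 where possible.
- Record the method and its start date at Visit 1, and any change at Visit 2.
- Repeat the proteomic and lipid analysis without women whose hormonal method began or changed near or after baseline. This can stand in the statistical analysis plan.

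The cost is a short amendment, two data fields, and a later Visit 1 for a few women. Section 5.0 expects recruitment to be easy, so that delay should be affordable. With no new starters (k = 0), the false-positive rate from this source returns to the nominal 5%.

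### Does leaving the endpoint open, then running a same-sample ELISA called confirmatory, require a change to the plan?

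*Protocol*

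**What the plan says.** Section 4.0 is a single sentence: "Specific endpoints have not been predetermined". The measurement is nevertheless defined. Section 6.0 sets the cohort at "40 patients (20 males and 20 females) aged 18-70 years", and section 1.0 describes them as patients "who will receive oral fenofibrate 160 mg/day for six weeks", so there is no untreated group. Section 10.0 (Visit 2) says "The plasma proteomic signature will be generated by LC-MS/MS (n=80 proteomes) of each subject before and after fenofibrate treatment" and gives the analysis family: "Bioinformatic approaches will then be employed based on geneset enrichment analysis to identify the biological processes/signaling networks impacted by treatment".

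The ELISA step appears in section 10.0 under both visits and again in section 11.0: "Samples will be stored in ultra-low freezers for proteomics and subsequent confirmatory assays (by ELISA"). No second cohort or held-out set is named, and no rule is given for choosing which proteins go to ELISA.

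On purpose, section 1.0 says "This will generate new hypotheses about the common root causes of diabetic complications". Section 5.0 begins its remark on size with "While our sample size is adequate for discovery research related to the systemic effects of fenofibrate treatment", and goes on to say that a study of outcomes would need many more people and longer follow-up.

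**The concern.** With no endpoint fixed and ELISA coming after proteomics, the natural reading is that proteins will be chosen because their change between visits looks large in these 40 people. Measuring them again in the same tubes removes some assay error. It does not remove the between-person sampling error behind the selection, nor any change over six weeks that has nothing to do with the drug.

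A reader who took the word confirmatory at face value could therefore credit the ELISA with replication that it does not provide. Some false leads would pass as confirmed, with effect sizes inflated by selection. Section 1.0 hopes that the work will lead eventually to targeted therapies or new uses for existing drugs, so misplaced trust in the candidate list would matter.

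**Working it through.** **Inputs from the protocol.** 40 participants (section 6.0), all treated (section 1.0), two visits, 80 proteomes (section 10.0). The protocol's one checkable figure reproduces: 40 × 2 = 80. It gives no significance level, power or effect size.

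**Assumptions, not in the protocol.** Number of proteins quantified, m = 200, 500 or 1000; correlation ρ between LC-MS/MS and ELISA change scores, 0.3 to 0.9; two-sided paired t-test at 0.05 for each protein; a pass at ELISA means p < 0.05 in the same direction.

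**Step 1: chance findings with unadjusted testing and no true effect.** Expected number = 0.05 × m, which is 10, 25 and 50 for m = 200, 500 and 1000.

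**Step 2: how many of these pass ELISA.** For new, independent people the theoretical rate is 0.05 / 2 = 2.5%. For the same samples the rate was simulated with 200,000 null proteins and n = 40 pairs:

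| ρ | Share passing | Of about 25 (m = 500) |
|---|---|---|
| 0 (new people) | 2.4% | 0.6 |
| 0.3 | 9% | 2.3 |
| 0.5 | 17.5% | 4.4 |
| 0.7 | 31% | 7.8 |
| 0.8 | 43.5% | 10.8 |
| 0.9 | 58% | 14.3 |

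Same-sample ELISA is thus a weaker filter than new participants at every non-zero correlation tried. It is still a filter, because some false findings drop out in every row.

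**Step 3: the same question with ordinary error control.** Take m = 500, 10% of proteins (50) truly shifted by 0.6 SD in both assays, and the Benjamini-Hochberg procedure at 5% on the LC-MS/MS results. About 38.2 true and 1.9 false proteins are listed, so the false share is 1.9 / (38.2 + 1.9) = 4.7%. After same-sample ELISA the false count is 0.6 (ρ = 0.5), 1.1 (ρ = 0.7) or 1.7 (ρ = 0.9). With no true effects at all, the list holds on average about 0.05 false proteins per study.

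**Step 4: change over time unrelated to the drug.** A drift of 0.2, 0.3 or 0.5 SD would be significant in 23%, 46% or 87% of paired tests at n = 40. ELISA on the same samples would see the same drift. So would a new cohort without a control group. This limit comes from the single-arm design and not from the choice of ELISA.

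**Step 5: what a change would alter.** Calling the ELISA step analytical verification moves no number in Steps 1 to 4. Only the error-control rule does: for m = 500 it is what separates the 25 chance findings of Step 1 from the 1.9 of Step 3.

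**The case for a change.** The strongest case for a change is that section 4.0 is not mere silence. It declares the endpoint open although Aim 2 and section 10.0 already say what is measured. Discovery data contain no confirmation step, so the word confirmatory is out of place, the more so beside a hypothesis in section 1.0 that attributes the changes to treatment. If only a technical cross-check was meant, the protocol could say so, at the cost of a few words. False discovery control does not rescue the ELISA either: at ρ = 0.9, about 1.7 of the 1.9 false proteins still pass.

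Part of this stands. Same-sample ELISA is not independent evidence, and with no control group neither assay can separate the drug from time. The word is loose.

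The rest does not carry. The adjective describes the assays, and checking a mass-spectrometry result by a second method is its usual laboratory sense. No section says that ELISA will confirm an effect of fenofibrate. An open endpoint fits a study that presents itself as hypothesis-generating and whose section 4.0 heading is marked as applying only where relevant. Large numbers of false leads arise only under unadjusted protein-by-protein testing, which no section plans; section 10.0 plans gene-set enrichment. That proteins will be chosen for ELISA from the data is likely, but it is an inference. The drug uses in section 1.0 are described as the ultimate impact of the work; the study's own products are a sample repository, a proteome characterisation and hypotheses.

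**Conclusion.** The observation is correct but calls for no change. ELISA in the stored samples verifies the LC-MS/MS measurement and adds no independent evidence that a change is real or due to fenofibrate. The protocol does not claim otherwise.

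The size of any harm depends on choices the document does not state. For 500 proteins it ranges from about 2 to 14 false proteins passing ELISA, if testing is unadjusted and none truly change, to about 0.6 to 1.7 with 5% false discovery control and one protein in ten truly shifted by 0.6 SD. The simulations also treat proteins as independent of one another.

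The items that would decide the matter are the paired test, the error rate, the enrichment ranking and the order of analyses. A statistical analysis plan commonly supplies these; none was available here, and analysts of paired proteomes would fill them in sensibly. What remains is a loose label whose correction would change no estimate and no error rate. The point to carry forward is one of reporting: agreement between the two assays should be described as analytical agreement, and confirmation of a treatment effect left to an independent, controlled sample.
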